Efficacy and Safety of Dapagliflozin in Acute Heart Failure

DICTATE-AHF

NCT 04298229

Protocol

A Randomized, Open-label Study of Dapagliflozin in Patients with or without Type 2 Diabetes Admitted with Acute Heart Failure

Principal Investigator:

[name] Director, HF and Transplant Section Vanderbilt Heart and Vascular Institute Vanderbilt University [name]

Co - Principal Investigator:

[name] Clinical Pharmacy Specialist Vanderbilt University [name]

Site Investigators:

[name]. – Vanderbilt University Medical Center [name]. - St Thomas Hospital System A. [name]. – Centennial Hospital [name] – University of Mississippi [name] – Integris Baptist Medical Center [name] – University of North Carolina

Clinical Coordinating Center:

[name]; [name]; [name]

Data Coordinating Center:

[name], [name], [name]

Sponsor:

Vanderbilt University Medical Center

PROTOCOL VERSION AND AMENDMENT TRACKING

Version Number/Amendment	Approval Date
1.4/ Original protocol	2.10.2020
2.0/Amendment One	1.4.2021
3.1/Amendment Two	6.14.2021
4.0/Amendment Three	9.21.2021

Abbreviations

Acute Decompensated Heart Failure			
B-type natriuretic peptide			
Blood pressure			
Clinical Coordinating Center			
Clinical Events Committee			
Data coordinating center			
Data and Safety Monitoring Board			
Emergency department			
Fractional excretion of sodium			
Heart failure with preserved ejection fraction			
Heart failure with reduced ejection fraction			
Intensive care unit			
Intravenous			
Left ventricular ejection fraction			
Principal Investigator			
Vanderbilt University Medical Center			
Worsening Heart Failure			

CLINICAL TRIAL SUMMARY

Title	A Randomized, Pilot Study of Dapagliflozin in Patients with or without Type 2 Diabetes Admitted with Acute Heart Failure
Study Objectives	The primary endpoint is to determine the cumulative change in weight (kilograms) per 40mg of IV furosemide equivalents from enrollment to day 5 or discharge (if earlier) between: 1) protocolized diuretic therapy and 2) dapagliflozin plus protocolized diuretic therapy guided by urine output.
	 Secondary endpoints include comparing differences among the two arms in the following: Incidence of worsening heart failure during hospitalization requiring IV inotropic therapy, new admission to an intensive care unit, new non-invasive positive pressure ventilation with bi-level positive airway pressure, or increase in the IV diuretic protocol intensity by 2 rows after Study Day 1 as adjudicated by the Clinical Event Committee Hospital readmission within 30 days of discharge for heart failure or diabetic reasons as adjudicated by the Clinical Event Committee
	 Exploratory endpoints include comparing difference among the two arms in the following: NT-proBNP at baseline to discharge adjusted for baseline Urine-output based Diuretic efficiency: 24-h total urine output (ml) per 40mg of IV furosemide equivalents on day 2 of IV diuretic therapy from 24-h urine collection (collected day 2-day 3) Fractional excretion of sodium (FENa)-based diuretic efficiency on day 2 of IV therapy: FENa per 40mg of IV furosemide equivalents of bolus loop dose using spot urine collected 2 hours after bolus loop dose Urinary Na/K ratio at day 2 of IV therapy adjusted for baseline Calculated 6-hour sodium output on day 2 of IV therapy using spot urine sodium collected 2 hours after bolus loop dose Length of hospital stay, measured as days from admission to discharge Presence of symptoms of congestion and dyspnea at discharge, measured via blinded-physician exam and patient reported congestion scores

	 Hospital readmission within 30 days of discharge for any cause Number of days at home without hospitalization or emergency room visit during 30-day follow up period Mean serum glucose during therapy Amount of total daily insulin doses (units) utilized per day during therapy among patients with diabetes, compared between treatment arms and to a prior to enrollment outpatient insulin regimen serum potassium covariate adjusted for baseline with attention to both elevation and depression
	 Safety endpoints from study medication administration to hospital discharge: estimated Glomerular Filtration Rate by the MDRD equation at discharge adjusted for baseline Incidence of ketoacidosis Serum glucose covariate adjusted for baseline with attention to both elevation (> 400mg/dl) and depression (< 70mg/dl) Incidence of hypovolemic hypotension, defined as symptomatic hypotension with a sustained systolic blood pressure less than 90 mmHg over 30 minutes requiring fluid administration Inpatient mortality
Study Design	This is a randomized trial of the addition of dapagliflozin to patients with or without diabetes hospitalized with AHF. Participants will be recruited following an initial standard evaluation in the ED and randomized within 24 hours of presentation for AHF in a 1:1 fashion to protocolized diuretic therapy or dapagliflozin + protocolized diuretic therapy.
Number of Participants	240 participants will be randomized
Trial Location	Up to six sites including but not limited to:
	 Vanderbilt University Medical Center St Thomas Hospital System Centennial Hospital University of Mississippi Integris Baptist Medical Center

	University of North Carolina
Inclusion	1) Age of 18 years or older
Criteria	2) Randomized within 24 of presentation during a hospital admission for hypervolemic decompensated heart failure defined as either:
	 pulmonary artery catheterization with a pulmonary capillary wedge pressure greater than 19mmHg plus a systemic physical exam finding of hypervolemia (peripheral edema, ascites, or pulmonary edema on auscultation) in the absence of pulmonary artery catheterization data 2 of the following signs or symptoms: peripheral edema, ascites, jugular venous pressure > 10mmHg, orthopnea, paroxysmal nocturnal dyspnea, 5-pound weight gain, or signs of congestion on chest x-ray or lung ultrasound
	3) Planned or current use of IV loop diuretic therapy during current hospitalizaiton
	4) eGFR \geq 25 ml/min/1.73m ² by the MDRD equation
Exclusion Criteria	Type 1 diabetes Serum glucose < 80mg/dl at enrollment Systolic blood pressure < 90mmHg at enrollment Requirement of intravenous inotropic therapy at enrollment or anticipated need of therapy during the study period History of hypersensitivity to any SGLT2 inhibitors Women who are pregnant or breastfeeding Severe anemia (Hemoglobin < 7.5g/dl) Severe uncorrected aortic or mitral stenosis Inability to perform standing weights or measure urine output accurately History of diabetic ketoacidosis Chronic combination nephron blockade with loop and thiazide therapy as an outpatient scheduled daily for more than 7 days prior to admission (Does not include HCTZ < 50mg for blood pressure) Diffuse anasarca with 4+ edema and projected hypervolemia exceeding 40-pounds Severe hepatic impairment (Child-Pugh class C if severity of hepatic failure is in question) Clinical picture consistent with acute myocardial infarction including troponin elevation or ischemic changes on electrocardiogram Site investigator determines the subject is not a good candidate to participate in study at this time

Primary Endpoint	cumulative change in weight (kilograms) per 40mg of IV furosemide equivalents from enrollment to day 5 or discharge (if earlier) between protocolized diuretic therapy and dapagliflozin plus protocolized diuretic therapy guided by urine output			
Assessment Schedule (Appendix A)	Baseline : standing weight, NT-proBNP, BMP, hemoglobin A1c, spot urine values of sodium, potassium, and creatinine (calculate urine sodium/potassium ratio, FENa), vital signs, study loop diuretic and diabetic medication orders, congestion score, document baseline HF and diabetic medications, start urine output quantification, urine biobanking for future investigations including urinary exosomes.			
	Daily: standing weight, BMP, vital signs, urine output quantification, titration of study loop diuretic and diabetic medication orders, document HF and diabetic medications, adverse event assessment			
	Day 2 : daily assessments as above plus 2-hour post loop diuretic spot urine sodium, potassium, and creatinine. Calculate FENa, 6-hr sodium output, urine sodium/potassium ratio, 24-hour urine collection for quantification and diuretic efficiency calculation, urine biobanking for future investigations including urinary exosomes.			
	Day 5 or Discharge: standing weight, NT-proBNP, BMP, vital signs, urine output quantification, document HF and diabetic medications, congestion score, outcomes assessment, remind primary team to schedule standard-of-care 3-7-day follow-up visit with endocrinology (if patient has diabetes) and HF			
	30-day phone follow-up : document HF and diabetic medications, outcomes assessment			
Study Duration	Enrollment is anticipated to occur over 14 months with the end of study occurring at hospital discharge and a 30-day phone-call follow-up			
Clinical Event Committee	The following events will be adjudicated by a Clinical Event Committee blinded to patient assignment:			
	 Worsening heart failure defined as inpatient administration of an IV inotrope with dobutamine, milrinone, or dopamine, new admission to an intensive care unit, new non-invasive positive pressure ventilation with bilevel positive airway pressure, or increase in the IV diuretic protocol intensity by 2 rows after Study Day 1 30-day hospital readmissions due to heart failure or diabetes- related events 			

	 Prolonged hospitalization as a result of hypoglycemia requiring medical intervention Prolonged hospitalization as a result of hypotension requiring medical intervention In-hospital incidence of ketoacidosis Inpatient mortality
Data and Safety Monitoring Board	An independent Data and Safety Monitoring Board will advise the principal investigator on safety aspects and overall progress of the study.

Table of Contents:

- **1.0** Background and rationale
- 2.0 Study outcomes
- 3.0 Inclusion/Exclusion criteria
- 4.0 Patient screening, consent, and randomization
- 5.0 Study Procedures
- 6.0 Risks
- 7.0 Reporting of adverse events
- 8.0 Data collection and record keeping
- 9.0 Study withdrawal
- 10.0 Statistical methods
- 11.0 References

1.0 Background and Rationale:

Patients with acute decompensated HF (ADHF) are generally admitted due to symptoms of congestion and 90% are treated with a loop diuretic.¹ However at least one-third of these patients are inadequately decongested due primarily to "diuretic resistance" and/ or "cardiorenal syndrome".^{2,3} The inability to achieve decongestion is associated with a worse prognosis and a higher rate of re-hospitalization for ADHF.² More than 40% of all patients admitted with ADHF have diabetes and that percentage is growing both in Heart Failure with Reduced Ejection Fraction (HFrEF) and Preserved Ejection Fraction (HFpEF).⁴

The admission blood glucose is elevated in approximately one-half of ADHF hospitalizations. ^{5,6} We recently demonstrated the admission blood glucose was within 50mg/dl of the chronic average blood glucose in 66% of patients with diabetes admitted with ADHF.⁷ The median (IQR) admission blood glucose change from the chronic blood glucose was only -7 (-29, 26) mg/dl.⁷ Thus, the acute glucose in patients with T2DM presenting with acute heart failure is most often related to poor chronic glucose control suggesting that these patients would benefit from attempts to initiate therapies to improve chronic glucose control while in the hospital.

No new therapies have been introduced in the United States for ADHF in several decades. Natriuretic peptides such as nesiritide and ularitide have failed to improve outcomes in either the chronic or acute heart failure patients.^{8,9} Diuretic resistance and hyperglycemia are common problems in ADHF admissions and represent a therapeutic opportunity for new therapies.^{5,10}

The sodium-glucose cotransporter-2(SGLT2) inhibitors, now approved for the antihyperglycemic therapies also have an osmotic diuretic and natriuretic effect.¹¹ In the chronic setting SGLT2 inhibitors reduce weight with modest decrements in systolic and diastolic blood pressure with a marked drop in albuminuria and a small drop in estimated GFR (-5 mL min⁻¹.1.73 m⁻²) which returns to baseline over time.¹¹ In patients with diabetes the SGLT2 transporter likely accounts for as much as 14% of total sodium chloride absorption. In the acute setting following a single dose, SGLT2 inhibitors did not increase urine volume.¹² However, the acute diuretic effects have not been studied in a population with heart failure with or without concomitant hyperglycemia who are undergoing diuresis. To our knowledge, no current trials are investigating the effects of SGLT2 inhibition in ADHF. The current studies planned in HF are investigating the acute effects of SGLT2 on stable HF (NCT03027960), the chronic effects of SGLT2 inhibition in compensated, chronic HF (NCT03619213, NCT02653482, NCT03030235, NCT03057977), changes in pulmonary pressure hemodynamics in patients monitored by CardioMEMs devices (NCT03030222), and effects on cardiopulmonary exercise fitness in chronic HF (NCT02862067).

Congestion remains the major cause of hospital readmission for heart failure and an inpatient plan of care that allowed more effective decongestion would be rapidly and widely adopted by the medical community. Therefore, we propose to test the

decongesting effects of the SGLT2 inhibitor dapagliflozin in patients with or without Type II diabetes admitted with an acute decompensation of chronic heart failure.

2.0 Study Outcomes:

- 2.1 Primary Outcome
- The change in weight in kilograms per 40mg of IV furosemide equivalents from enrollment baseline to day 5 or discharge (if earlier)
 - Standing weights will be performed by study personnel using the same scale throughout the study period with the same clothing (hospital gown without shoes). The patient will be requested to empty their bladder and bowels if needed prior to each weight assessment.
 - The cumulative loop diuretic dose includes all IV and oral doses administered in the study period, converted to IV furosemide equivalents. Diuretic conversion: 80mg oral furosemide = 40mg IV furosemide = 20mg oral torsemide = 1mg oral/IV bumetanide

This primary outcome investigates the decongestive potential of dapagliflozin by its impact on diuretic efficiency. Higher diuretic efficiency has been associated with better outcomes in multiple AHF populations.^{13,14} The primary outcome does not quantify the importance of initiating a mortality reducing therapy during hospitalization, which increases chronic adherence. Therefore, even if dapagliflozin does not meet the primary endpoint, this study would still be beneficial to establish the safety and best practices of initiating dapagliflozin during an AHF hospitalization, setting the stage for continuing it into the outpatient setting. The established benefits of such a strategy would emerge over the coming months to years. In addition to mechanistic and diuretic endpoints, additional secondary outcomes are designed to establish the safety across hemodynamic, renal, and glycemic outcomes.

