- Amount of total daily insulin doses (units) utilized per day during therapy among patients with type 2 diabetes, compared between treatment arms and to a prior to enrollment outpatient insulin regimen
- serum potassium covariate adjusted for baseline with attention to both elevation and depression

Single-Center Exploratory Outcomes at Vanderbilt University Medical Center

The following exploratory outcomes will only be performed in patients at Vanderbilt University Medical Center who elect to participate in a sub-study. Patients can decline to participate in this sub-study and still participate in parent clinical trial. To explore changes in the plasma proteome during IV diuresis, we will collect one 15mL blood sample (10mL in purple top EDTA tube and 5mL in red top tube) at baseline and on the final study day (Day 5 or discharge).

2.4 Safety Outcomes: Compared between treatment arms during the index stay from signing of informed consent to hospital discharge

- Change in the estimated Glomerular Filtration Rate by the MDRD equation at discharge adjusted for baseline
- Incidence of ketoacidosis, identified by the study team as elevated ketones in the urine and an arterial blood pH < 7.35 and adjudicated by the Clincal Events Committee
- Serum glucose covariate adjusted for baseline with attention to both elevation (> 400mg/dl) and depression (< 70mg/dl)
- Potential prolonged hospitalization as a result of hypoglycemia requiring medical intervention as adjudicated by the Clinical Events Committee
- Potential prolongation of hospitalization as a result of incidence of hypovolemic hypotension, defined as a symptomatic hypotension with a sustained systolic blood pressure less than 90 mmHg over 30 minutes and requiring medical intervention as adjudicated by the Clinical Events Committee. All hypotension episodes requiring medical intervention will be evaluated by the Clinical Events Committee.
- Inpatient mortality

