5.1 Diabetic Therapies for patients with a diagnosis of Type 2 diabetes

After enrollment, all previous diabetic therapies will be discontinued. Patients will be randomzed in a 1:1 ratio to standard of care with protocolized diuretic therapy or standard of care with protocolized diuretic therapy plus the addition of open label SGLT2 inhibitor therapy with dapagliflozin 10 mg orally once daily for the duration of the study, which will be until 5 days or hospital discharge. The patient will receive standard

of care point of care blood glucose monitoring 4 times daily (before meals and at bedtime) and correctional insulin according to a blood glucose scale. For patients requiring large doses of basal insulin, the patient will be continued on a reduced dose of basal insulin. Insulin initiation and titration algorithms are in Appendix B.

Non-insulin hypoglycemic: chronic, outpatient oral hypoglycemic medications which may include but are not limited to sulfonylureas, DPP-4 inhibitors, and/or metformin.

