6.0 Risks

[figure not shown]
This study will evaluate the addition of oral dapagliflozin to standard-of-care heart failure therapies in patients with hypervolemic heart failure. We do not expect the risk of the dapagliflozin treatment arm will be different than the standard of care treatment arm. Dapagliflozin has a lower hypoglycemia risk than standard of care insulin therapy. Study procedures are designed to manage and minimize risks through careful selection of the patients who participate in the trial. We have developed a standardized protocol for diabetic therapies with endocrinology to minimize hypoglycemia risk in patients with diabetes. Participants will be monitored throughout the treatment phase of the study, throughout hospitalization, and at 30-day follow-up. Further, an independent DSMB will monitor safety of the participants throughout the study.

7.0 Reporting of Adverse Events or Unanticipated Problems involving Risk to Participants or Others

An Adverse Event (AE) is the development of an undesirable medical condition or the deterioration of a pre-existing medical condition following or during exposure to a

pharmaceutical product, whether or not considered causally related to the product. An undesirable medical condition can be symptoms (eg, nausea, chest pain), signs (eg, tachycardia, enlarged liver) or the abnormal results of an investigation (eg, laboratory findings, electrocardiogram). In clinical studies, an AE can include an undesirable medical condition occurring at any time, including run-in or washout periods, even if no

study treatment has been administered. The term AE is used to include both serious and non-serious AEs. The time period of AE evaluation in this study will start after signature of the informed consent and will conclude at the end of the follow up period 30 days after hospital discharge.

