 - a. Repeated as per doubling of the cumulative Day 2 loop diuretic dose (log2 cumulative loop diuretic dose centered at 40mg)
- d) Spot urine sodium-based diuretic efficiency defined as the spot urine sodium concentration (mmol/L) on Day 2 per 40mg of IV furosemide equivalents (preceding loop diuretic dose)
- e) Fractional excretion of sodium (FENa)-based diuretic efficiency on Day 2 of IV therapy defined as the FENa from a spot urine test on Day 2 of IV therapy collected ~2 hours after bolus loop dose per 40 mg of IV furosemide equivalents.
 - a. Repeat as per doubling of the cumulative loop diuretic dose (log2 cumulative loop diuretic dose centered at 40mg)
- f) Urinary Na/K ratio at Day 2 of IV therapy adjusted for baseline.
- g) Calculated 6-hour sodium output on Day 2 of IV therapy using spot urine sodium collected 2 hours after bolus loop dose.
- h) Length of hospital stay, measured as days from admission to discharge
- i) Presence of symptoms of congestion and dyspnea at discharge, measured via blinded-physician exam and patient reported congestion scores.
- j) Hospital readmission within 30 days of discharge for any cause.
- k) Number of days at home without hospitalization or emergency room visit during 30-day follow up period.
- 1) Mean serum glucose during therapy
- m) Amount of total daily insulin doses (units) utilized per day during therapy, compared between treatment arms and to a "prior to enrollment" outpatient insulin regimen.
- n) Analyze the change in basic metabolic panel laboratory values and hemoglobin from baseline to end of study
- o) Serum potassium covariate with attention to both elevation and depression.

Hypokalemia levels are defined as

- a. Not hypokalemic: serum potassium > 3.4 mEq/L
- b. Mild: serum potassium 3.0 3.4 mEq/L
- c. Mod-Severe: serum potassium < 3.0 mEq/L

Hyperkalemia levels are defined as

- a. Not hyperkalemic: serum potassium < 5.1 mEq/L
- b. Mild: serum potassium 5.1 5.5 mEq/L
- c. Severe: serum potassium > 5.5 mEq/L

Safety Endpoints: Comparing differences among the two arms in the following:

- a) Estimated Glomerular Filtration Rate by the MDRD equation at discharge adjusted for baseline. A sensitivity analysis of eGFR by the CKD-EPI equation will also be done.
- b) Incidence of ketoacidosis as adjudicated by the CEC
- c) Serum glucose with attention to both elevation and depression.
 - a. Hypoglycemia is defined as:
 - i. Not hypoglycemic: serum glucose > 70 mg/dl

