- h) The association of length of hospital stay with treatment assignment will be analyzed using the Wilcoxon Rank Sum test

- The association of presence of symptoms of congestion and dyspnea at discharge measured via blinded physician exam and patient reported congestion scores with treatment assignment will be analyzed using the Pearson chi-square test. A proportional odds model will be used to assess the association of discharge congestion score with treatment assignment, adjusting for baseline congestion.
- j) Cumulative incidence of all cause hospital readmission within 30 days of index hospitalization discharge will be graphed by treatment arm treating death as a competing risk. The association of all cause hospital readmission within 30 days of index hospitalization discharge with treatment assignment will be analyzed using the Pearson chi-square test.
- k) The association of number of days at home without hospitalization or emergency room visit during the 30-day follow-up period with treatment assignment will be analyzed using the Wilcoxon Rank Sum test. For purposes of analysis, subjects who died within 30 days of the index hospital discharge will be assigned a value of 0 days at home
- 1) The association of mean serum glucose during therapy with treatment assignment will be analyzed using the Wilcoxon Rank Sum test
- m) Total daily insulin doses (units) utilized per day during therapy will be compared between treatment arms in all comers and in those with diabetes at baseline using a Wilcoxon Rank Sum Test. Total daily insulin doses utilized per day during therapy will be compared to a 'prior to enrollment' utilization using the Wilcoxon Signed Rank Test.
- n) The change in basic metabolic panel laboratory values and hemoglobin from baseline to the end of study will be compared across treatment groups using the Wilcoxon Rank Sum test.
- o) Serum potassium trends over time by treatment assignment will be graphed. Descriptive statistics
 of the daily raw potassium values and kalemic status during hospitalization by treatment group
 will be reported and compared across treatment assignments by Wilcoxon Rank Sum tests and
 Pearson's chi-square tests, respectively.

Safety Analyses:

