All multivariable models will adjust for the same key covariates as specified for the primary outcome, as sample size permits. Appropriate model diagnostics will be run to assess model fit. If model diagnostics suggest the planned approach violates necessary assumptions, alternative methods will be pursued.

- a) The association of estimated Glomerular Filtration Rate (eGFR) at discharge, calculated using the MDRD equation, with treatment assignment will be modeled using covariate-adjusted PO regression, adjusting for baseline eGFR. The analysis will be repeated calculating eGFR using the CKD-EPI equation as well.
- b) The association of the incidence of ketoacidosis as adjudicated by the CEC with treatment assignment will be analyzed using the Pearson chi-square test.
- c) Serum glucose trends over time by treatment assignment will be graphed. Descriptive statistics of the daily raw glucose values and the glycemic status during hospitalization by treatment group will be reported and compared across treatment assignment by Wilcoxon Rank Sum tests and Pearson's chi-square tests, respectively.
- d) The association of incidence of hypovolemic hypotension, defined previously, with treatment assignment will be analyzed using the Pearson chi-square test.

e) The association of inpatient mortality with treatment assignment will be analyzed using the Pearson chi-square test and univariate logistic regression.

Sensitivity Analyses:

Our sensitivity analysis will be a covariate-adjusted proportional odds (PO) regression model with our outcome being log-transformed weight at the minimum of Day 5 or discharge and the main predictor being treatment assignment. Adjusting covariates will be as defined in the primary analysis. Appropriate model diagnostics will be run to assess model fit. If model diagnostics suggest the planned approach violates necessary assumptions, alternative methods will be pursued.

Heterogenicity of Treatment Effect:

Heterogenicity of Treatment Effect (HTE) will be assessed refitting the primary model with the covariate of interest interacted with treatment assignment. The HTE analysis will include the following variables:

- Sex (male or female)
- Baseline edema score (No-Mild/Moderate/Severe)
- Baseline NTproBNP
 - Continuous
 - Dichotomize by median NTproBNP [above/below]
- Baseline BMI-adjusted BNP: defined as a 4% increase in NT-proBNP for every 1 unit increase in baseline BMI above a BMI of 20kg/m²
 - Continuous

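### The safety endpoints have two different start points in the protocol and none in the SAP, and they stop at discharge, so in-hospital events are compared without regard to time at risk and 30-day deaths and adverse events enter no safety comparison

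*Protocol*

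**What the plan says.** **Start.** The Clinical Trial Summary runs the safety endpoints "from study medication administration to hospital discharge". Protocol section 2.4 has them "Compared between treatment arms during the index stay from signing of informed consent to hospital discharge". The SAP heading reads only "Safety Endpoints: Comparing differences among the two arms in the following" and gives neither a start nor an end, although some items under it are tied to discharge or to the inpatient stay.

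**Treatment.** The control arm receives protocolized diuretic therapy with no dapagliflozin and no placebo (SAP, Treatment arms). Dapagliflozin is given "for the duration of the study, which will be until 5 days or hospital discharge" (protocol section 5.1), so a hospital stay can outlast dosing.

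**Analysis.** The SAP (Safety Analyses) compares ketoacidosis and hypovolemic hypotension by Pearson chi-square. For death: "The association of inpatient mortality with treatment assignment will be analyzed using the Pearson chi-square test and univariate logistic regression". Length of stay is compared between arms as an exploratory endpoint.

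**After discharge.** Adverse-event evaluation starts after consent and will "conclude at the end of the follow up period 30 days after hospital discharge" (protocol section 7.0). Section 7.4 lists death among the events to be reported. The SAP uses post-discharge deaths as a competing risk in the readmission cumulative incidence plots, and in the days-at-home analysis: "subjects who died within 30 days of the index hospital discharge will be assigned a value of 0 days at home". It specifies no by-arm comparison of 30-day mortality and no by-arm table of adverse or serious adverse events.

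**The concern.** Protocol section 2.1 says the trial remains worthwhile if the primary endpoint is missed, because it will establish the safety of starting dapagliflozin in hospital. Safety is therefore the fallback conclusion, and its window should be unambiguous and the same in both arms.

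Three things stand in the way. An analyst working from the SAP must choose between two start points. The end of the window is a date that treatment could change: the trial hypothesises better decongestion, treatment is open-label, and length of stay is itself an outcome. An arm that goes home sooner has fewer days in which an in-hospital event can be counted. Finally, the follow-up that would remove this dependence is collected, but no planned safety comparison uses it.

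**Working it through.** No stated sample size, power or event count rests on the safety window, so there is no figure in the plan to reproduce. The check is a comparison of the texts, followed by an illustration on assumed inputs.

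**1. Start of the window**

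- *Summary wording, study medication read as dapagliflozin:* the start exists in one arm only.
- *Summary wording, study medication read as the protocol loop diuretic:* both arms have a start, but section 5.3.1 allows loop doses before randomisation, so the window may open before assignment.
- *Section 2.4 wording:* the start exists in both arms. It also precedes randomisation, so events that treatment cannot have caused may be counted. Randomisation balances these on average; they add noise, not bias.

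The start conflict would bias a comparison only if the arms were given different starts. The delay from consent to first dose is not stated. If it were 2 to 24 hours (assumed), it would be 2/120 = 1.7% to 24/120 = 20% of a 5-day (120-hour) stay.

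**2. End of the window**

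The documents give no daily event rate and no expected stay, so both are assumed. Let every patient in an arm have the same stay of d days and both arms the same constant daily hazard h. Then risk = 1 − exp(−h·d). The first row uses a daily risk of 0.2% compounded: 1 − 0.998^6 = 1.19% and 1 − 0.998^7 = 1.39%.

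| Assumed daily rate | Stays (days) | Risk | Ratio | Expected events per 120 |
|---|---|---|---|---|
| 0.2% | 6 vs 7 | 1.19% vs 1.39% | 0.86 | 1.43 vs 1.67 |
| 0.5% | 5 vs 6 | 2.47% vs 2.96% | 0.835 | 3.0 vs 3.5 |
| 1% | 5 vs 6 | 4.88% vs 5.82% | 0.837 | 5.9 vs 7.0 |
| 2% | 5 vs 6 | 9.52% vs 11.31% | 0.842 | 11.4 vs 13.6 |
| 1% | 5 vs 7 | 4.88% vs 6.76% | 0.721 | 5.9 vs 8.1 |
| 1% | 5 vs 5 | 4.88% vs 4.88% | 1.00 | 5.9 vs 5.9 |

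At low rates the ratio is close to the ratio of the stays (5/6 = 0.83, 6/7 = 0.86), so it depends little on h. The absolute difference depends on h a great deal: at 0.2% per day it is 1.67 − 1.43 = 0.24 of a death per 120.

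This applies to inpatient mortality, ketoacidosis and hypovolemic hypotension, which are incidences over the stay. It does not apply to eGFR at discharge, which is a value at one time point.

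**3. Data collected against data compared**

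Deaths and adverse events are collected to 30 days after discharge. The listed safety endpoints use them only up to discharge. Later deaths enter two readmission plots and one exploratory score, and adverse events as such enter no planned comparison. Discharge cannot precede randomisation, so the contact 30 days after discharge already covers a fixed window of 30 days from randomisation.

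**The case against.** The strongest reply is that this is a one-line mismatch between a summary and the body of the protocol. Section 2.4 gives both arms the same consent start, and sections 7.0 and 7.4 use it for adverse events. A reader might infer from the summary that control patients have no start at all, or that the start conflict itself gives the arms different time at risk. The documents support neither: nothing says that the arms will use different starts, and a shared consent start is balanced by randomisation. That part of the reply stands.

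Ending at discharge can also be defended as matching the stated aim of showing safe initiation in hospital, since dosing stops at Day 5 or discharge. A 30-day window does add time off study drug. This supports keeping the in-hospital endpoints, but it does not make a comparison of proportions over unequal stays sound.

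A reader might further infer that a death soon after discharge is lost. It is not: it is reported as an adverse event, adverse-event reports go to the DSMB, and the death affects days at home and the competing-risk plots. What is missing is a by-arm safety comparison.

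Lastly, Appendix A has no column between Day 5 or discharge and the 30-day contact, so one might conclude that patients who stay longer go unobserved. The rest of the protocol does not bear this out. The summary lists adverse-event assessment among the daily tasks, section 6.0 provides monitoring throughout hospitalization, section 7.4 collects all adverse events through 30 days, and the Clinical Event Committee reviews in-hospital ketoacidosis and inpatient deaths (section 5.4).

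**Conclusion.** The point holds in three limited parts. The protocol gives two start points for the same endpoints and the SAP does not settle which applies. The common end at discharge lets time at risk differ by arm for three incidence endpoints that are analysed without regard to it. Deaths and adverse events collected to 30 days after discharge have no planned by-arm safety comparison.

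The discharge end, not the start conflict, is the main possible source of unequal time at risk. Its size cannot be derived from the documents. Under equal constant hazards, a one-day difference in stay gives a ratio of about 0.84 to 0.86, a two-day difference (5 against 7 days at 1% per day) gives 0.72, and equal stays give 1.00. It would be wrong to read the 0.86 as a 14% spurious reduction to be expected in this trial: it rests on an assumed rate and assumed stays, and amounts to about a quarter of a death per 120. Constant hazard is a further assumption; late days in hospital may carry less risk than the acute phase. The primary analysis and the sample size are not affected.

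**What to change.** - Reconcile the Clinical Trial Summary with section 2.4, and state in the SAP one safety window that starts at randomisation in both arms.
- Add all-cause death through 30 days from randomisation, compared by arm, as a safety endpoint. Keep inpatient mortality as descriptive.
- Add to the SAP a by-arm table of the adverse and serious adverse events already collected through 30 days after discharge.
- Ketoacidosis and hypotension would remain in-hospital incidences, so report days in hospital by arm beside them. Length of stay is already analysed.

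No extra chart review after Day 5 is needed as a separate change, because adverse-event collection already runs through 30 days after discharge.

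The cost is protocol and SAP wording, one more comparison and one more table, all from data the trial already collects. The downside is that a 30-day window includes time after study dosing has ended; keeping the inpatient figure beside it lets the reader see both.
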